14.1 General Considerations

General considerations: continuous variables will be summarized as n, mean, standard deviation, median, minimum and maximum. Categorical variables will be summarized as the number and percentage of patients in each category.

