2.1 Primary Objectives

Endpoint #1: Patient safety

The Primary Objective of this pilot study is to evaluate the safety of 90Y RE for the treatment of thrombocytopenia in the setting of cirrhosis. Primary Safety Endpoints include:

1. Assess safety of splenic administration of 90Y. [i.e. the onset of AEs such as infection or abscess as assessed by NCI Common Toxicity Criteria for Adverse Events (CTCAE) Version 4.0.3.)]

2. Assess the utility of splenic 99mTc-MAA injection to determine shunting prior to 90Y RE.

3. Assessment of short-term and long-term post-procedure events

Endpoint #2: Objective clinical endpoints

1. To achieve a 50% increase in platelet count six months after therapy. This will be assessed via CBC with differential at all study visits.

2. To achieve a 20% decrease in functional splenic volume six months after treatment.This will be assessed via cross-sectional CT or MR of the abdomen at screening and at4 weeks, three months, and six months after 90Y infusion.

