3.2.9. Previous randomization in a trial using 90Y RE

3.2.10. Patient must not have participated or enrolled in a clinical trial with an investigational

device / therapy within 30 days prior to randomization

3.2.11. Any serious medical condition likely to impede successful completion of the study,

such as certain mental disorders, cardiac arrhythmias, and uncontrolled

congestive heart failure or respiratory disease.

3.2.12. Patients actively on chemotherapy.

STATISTICAL CONSIDERATIONS

All patients will be accounted for in the final analysis. All patients who discontinue or withdraw after enrollment and before reaching the final follow-up period will be summarized by their reason for discontinuation/withdrawal and will contribute to the analyses as described below and in the statistical analysis plan.

Since this is an exploratory point of care study, the 20 patients are being used to look for a signal. Thus, a Simon's statistical design will not be utilized.

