12.2 Sample Size Determination

As a proof-of-pilot study, the primary rationale is safety. Once the patients are studied, secondary hypotheses may be generated to better refine patient selection and clinical applicability. Though missing data points may occur, statistical analysis will be conducted with the available acquired information.

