12.3 Demographics

Descriptive statistics of demographics, medical history, disease severity, time from diagnosis, physical exam, and other baseline characteristics will be presented for all patients.

Efficacy

Descriptive statistical analyses will be used for the safety and efficacy.

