12.5 Safety and Outcome Analysis

Clinical and outcome measures will be compared to baseline. These include platelet count and splenic volume.

Safety measures will be monitored at each study visit. These include the adverse event reporting;

physical examination; and cross-sectional imaging to assess for radio-pathologic findings. MAA will be conducted for the first four patients. The lung shunt study data will be provided to the FDA for review when all 4 patients have completed the lung shunt study before the 5th patient is scheduled for 90Y therapy. If average shunt of first four patients is less than 5%, then all subsequently enrolled patients will not undergo MAA. If average shunt is >5%, the next 6 patients will undergo MAA. If the average shunt among the 10 patients is >5%, then all subsequent patients will undergo MAA. Otherwise, the remaining patients will not receive MAA. In addition to the conventional angiogram, we will perform 3-dimensional rotational angiography/cone beam computerized tomography in all patients. Conventional angiography and cone beam CT essentially eliminate the chance of aberrant deposition of the radioactive microspheres. Subjects who do not undergo pretreatment MAA will undergo post-treatment 90Y PET scan.

Interim Analysis

An interim analysis will be performed after the 10th patient is enrolled. It will include patient registration, treatment and follow-up information including any adverse events and any concomitant medications which were taken due to study treatment and/or procedures per treating investigator. It will summarize the results of the primary and secondary objective clinical endpoints. Any protocol deviations will be listed as well.

STATISTICAL ANALYSIS

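### Long-term events are a primary safety endpoint, but with no window, denominator or use of follow-up time stated, their percentage is biased whenever follow-up is incomplete

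*Combined protocol and SAP*

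**What the plan says.** Section 2.1 (Endpoint #1, item 3) lists "Assessment of short-term and long-term post-procedure events" among the primary safety endpoints. It does not say where short-term ends and long-term begins, or which statistic will be reported.

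The statistical sections then say the following.

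- Under the Efficacy heading that follows 12.3: "Descriptive statistical analyses will be used for the safety and efficacy".
- Section 14.1, for every categorical variable: "Categorical variables will be summarized as the number and percentage of patients in each category".
- Section 14.4, on safety and outcome, is one sentence about comparison with baseline. It does not mention adverse-event rates.
- Section 12.5: "Safety measures will be monitored at each study visit".
- The opening paragraph of Statistical Considerations: "All patients will be accounted for in the final analysis". It adds that those who leave early are tabulated by reason and "will contribute to the analyses as described below and in the statistical analysis plan".
- Section 12.2, on missing data: "statistical analysis will be conducted with the available acquired information".

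Nothing that follows in sections 12 or 14, as shown, says how an early leaver contributes to the long-term event percentage. The interim analysis, placed after the 10th enrolment, also reports follow-up and adverse events, and again no rule is given for patients with little follow-up.

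**The concern.** A late event can be seen only in a patient who is still being observed. A percentage of all patients treats someone lost at week 4 in the same way as someone followed throughout without an event. The most direct reading of 14.1 together with the opening of Statistical Considerations is events over all 20 patients, which would understate late toxicity when patients withdraw or are lost.

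The same happens without any dropout at an interim look, because the newest patients have had no time in the long-term period.

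Section 12.2 names safety as the main reason for the study, and 14.2 expects the results to inform a later randomized trial. An ill-defined late-event rate would carry forward into that planning.

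**Working it through.** The plan states no event, withdrawal or death rate and no figure for this endpoint, so there is nothing to reproduce. What follows shows direction and size under stated assumptions.

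**Inputs.** From the documents: N = 20 (14.2) and an interim analysis after the 10th enrolment. Assumed: late-event risk F = 20% with no death or withdrawal; withdrawal W of 10 to 30%; deaths D of 0 to 20%; constant hazards over the period; withdrawal independent of toxicity.

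**Formulas.** Put a = −ln(1−F), w = −ln(1−W), d = −ln(1−D) and T = a + w + d.

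- Crude percentage, events over all patients: (a/T)(1 − e^(−T)).
- Cumulative incidence with death competing: (a/(a+d))(1 − e^(−(a+d))).
- Completers' percentage: crude / (crude + e^(−T)). The denominator is patients with an event plus those event-free at the end of the period.

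**1. Withdrawal only (D = 0, cumulative incidence 20.0%).** For W = 20%, a = w = 0.2231 and e^(−T) = 0.8 × 0.8 = 0.64. The crude figure is 0.5 × 0.36 = 18.0%, and the completers' figure is 0.18/(0.18 + 0.64) = 22.0%.

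| W | Crude | Crude / cumulative incidence | Completers |
|---|---|---|---|
| 10% | 19.0% | 0.95 | 20.9% |
| 20% | 18.0% | 0.90 | 22.0% |
| 30% | 16.9% | 0.85 | 23.2% |

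With F = 10% the ratios of crude to cumulative incidence are nearly the same.

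**2. Death only (W = 0).** The first two formulas become identical. For D = 10% both give 19.0%, and for D = 20% both give 18.0%, a ratio of 1.00. The crude figure is lower only than the 20.0% that would apply if nobody died.

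**3. Both (W = 20%, D = 20%).** The crude figure is 16.3% and the cumulative incidence 18.0%. Excluding event-free leavers and event-free deaths gives 24.1%. Two analysts who both follow the plan could therefore report 16.3% or 24.1% for the same expected data.

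**4. Everyone who withdraws does so before the window opens.** Assume a six-month risk of 30% and a window from month 1 to month 6, with h = −ln(0.7)/6. The risk in those still followed is 1 − e^(−5h) = 25.7%. Over all 20 patients it becomes 25.7% × 17/20 = 21.9% with 3 withdrawn at one month, and 25.7% × 15/20 = 19.3% with 5. The relative shortfall equals the share already gone (15% and 25%).

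**5. Interim.** If the data are cut when the 10th patient has just been enrolled, at most 9 of 10 can have entered the long-term period. A percentage over 10 is then at most 9/10 of the risk in those observed, before any dropout.

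**6. Precision.** Two events with 4 patients lost give 2/20 = 10.0% (exact 95% interval 1.2 to 31.7%) or 2/16 = 12.5% (1.6 to 38.3%). Even 0/20 has an upper 95% bound of 16.8%.

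**The case against.** A reader might infer that the plan counts patients who die or leave early as free of late events, so that late toxicity is understated. The documents do not support this.

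- **Coding.** Section 14.1 is a general rule without a denominator, and no sentence codes leavers as event-free. The wording on available information in 12.2 allows a denominator of patients actually observed, or of completers. The direction of error is therefore not fixed.
- **Death.** A patient who dies without a late event cannot have one. Counting that patient without the event is correct for cumulative incidence, so deaths alone do not make the treatment look safer on that measure.

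Two further objections carry weight. The document as shown moves from section 3 to section 12 and omits section 13, so a follow-up schedule or adverse-event section may define the window. And this is a descriptive pilot of 20 patients that already tabulates early leavers by reason, with intervals far wider than the shifts computed above.

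These points limit the size and certainty of the concern but do not remove it. Tabulating reasons shows who left, but not how much time at risk was lost. Imprecision is no reason to leave the denominator open until the data have been seen. Both obvious denominators, all patients and completers, are biased when follow-up is incomplete.

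**Conclusion.** The concern holds in a limited form. The statistical sections shown give a primary safety endpoint no time window, no denominator and no use of follow-up time. Under the all-patients reading, the late-event rate is too low when patients withdraw, are lost or have not yet reached the long-term period. The shortfall is about 5 to 15% in relative terms for 10 to 30% withdrawal spread over the period, and more if withdrawals come before the window opens. Under the completers' reading the rate is too high. Deaths alone cause no bias in the crude percentage as an estimate of cumulative incidence.

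These sizes rest on assumed risks, constant hazards and withdrawal unrelated to toxicity, none of which the documents give. In a 20-patient pilot this is a cheap improvement and does not threaten the study's purpose.

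**What to change.** Extend 14.4 to say the following.

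1. Short-term and long-term events are tabulated in separate windows, with the boundary and the end of the long-term window stated (or cross-referenced, if another protocol section defines them).
2. The denominator for each window is the number of patients alive and under follow-up at its start, shown with patient-months of follow-up in that window.
3. Beside the crude number and percentage, the cumulative incidence of infection or abscess, and of any serious event, is estimated by Aalen-Johansen. Death is a competing event; withdrawal, loss and follow-up not yet elapsed at the data cut are censored.
4. The same rules apply at the interim analysis.

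Item 3 is needed as well as item 2, because a start-of-window denominator still counts patients who withdraw inside the window as though fully observed.

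The cost is a paragraph of SAP text and one extra table. It needs dates of event, death and last contact, which the sponsor should confirm are recorded. Estimates from 20 patients will be imprecise, and the reported late-event rate may be slightly less favourable.

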14.2 Sample Size Accrual

This is a single center pilot study aiming to evaluate the safety, efficacy, and tolerability of 90Y RE for cirrhosis-associated thrombocytopenia. A small number of subjects will be recruited for this purpose (20 subjects). The first 4 subjects will receive planning angiography and MAA. They will be carefully monitored for adverse events to establish preliminary safety of initial dosing plan. The lung shunt study data will be provided to the FDA for review when all 4 patients have completed

the lung shunt study before the 5th patient is scheduled for 90Y therapy. We estimate it will take approximately 6 years to recruit, treat, and complete follow up on 20 subjects. The results of the study will provide critical preliminary data to later guide in powering a more statistically robust, and larger randomized controlled trial in the future.

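### The stated condition before patient 5 receives 90Y rests on pre-treatment lung-shunt data, not on how the first four patients tolerated the dose

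*Combined protocol and SAP*

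**What the plan says.** Section 14.2 gives the first four patients a safety purpose as well as a shunt purpose: "They will be carefully monitored for adverse events to establish preliminary safety of initial dosing plan".

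Sections 12.5 and 14.2 then set a condition at patient 5. In 12.5 it reads: "The lung shunt study data will be provided to the FDA for review when all 4 patients have completed the lung shunt study", and this is to happen "before the 5th patient is scheduled for 90Y therapy". The shunt result drives one decision: "If average shunt of first four patients is less than 5%, then all subsequently enrolled patients will not undergo MAA". A higher average extends MAA to the next six patients.

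Two other provisions bear on adverse events. Section 12.5 states: "Safety measures will be monitored at each study visit". The Interim Analysis paragraph that follows states: "An interim analysis will be performed after the 10th patient is enrolled". Of its content it says: "It will include patient registration, treatment and follow-up information including any adverse events". No action is attached to that analysis.

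Section 2.1 places the MAA shunt assessment before 90Y, names infection and abscess as examples of the safety events, and schedules cross-sectional imaging at 4 weeks, 3 months and 6 months after 90Y. Section 12.2 gives safety as the main reason for the study. On timing, 14.2 says: "We estimate it will take approximately 6 years to recruit, treat, and complete follow up on 20 subjects".

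**The concern.** The lead-in is meant to support a conclusion about the starting dose plan, but the condition that ends it uses data that cannot support that conclusion. A lung-shunt fraction is obtained before any 90Y is given. It informs whether later patients need MAA. It does not show whether treated patients developed infection, abscess or another reaction, which can be judged only after 90Y.

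Followed literally, the condition depends on four completed shunt studies and on sending the data. It does not require that patient 4 has been treated, or that any of the four has been observed for a given time. The available text names no reviewer, observation window or criterion for the safety judgement. Patient 5 could therefore receive the same dose plan before anyone has looked at the four patients together and recorded that the plan is acceptable.

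**Working it through.** The core of the point is a reading of the text and needs no calculation. The plan gives no power, event rate or other figure to reproduce. The arithmetic below asks how often the gap would matter and what a four-patient review could show.

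**Inputs from the plan.** 20 patients; 72 months to recruit, treat and follow up (study summary, 14.2); 4 patients in the lead-in; imaging 4 weeks after 90Y (2.1); interim analysis after patient 10.

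**Assumptions, not in the plan.** Follow-up of 6 months (12 as a check); 0–4 weeks from MAA to 90Y; patient 5 has no MAA; no time for FDA review; for random arrivals, exponential gaps. Weeks convert to months by 7/30.4375.

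**Pace.** (72 − 6)/20 = 3.3 months = 14.3 weeks per patient. With 12-month follow-up, (72 − 12)/20 = 3.0 months = 13.0 weeks.

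**Even accrual.** When patient 5 is ready, patient 4 has 14.3 − 0 = 14.3 weeks or 14.3 − 4 = 10.3 weeks since 90Y. Patients 1–3 have more. All four have passed 4 weeks.

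**Random arrivals.** Patient 5 is ready before patient 4 reaches 4 weeks after 90Y if the gap between them is shorter than w, the MAA-to-90Y interval plus 4 weeks. P = 1 − exp(−w/3.3), with w in months:

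| MAA-to-90Y interval | w | P |
|---|---|---|
| 0 weeks | 4 weeks = 0.920 months | 24.3% |
| 4 weeks | 8 weeks = 1.840 months | 42.7% |

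- If patient 5 also has MAA with the same interval, the intervals cancel and 43% falls to 24%. Any FDA review time that delays patient 5 lowers both figures.
- With 12-month follow-up the two figures are 1 − exp(−0.920/3.0) = 26% and 1 − exp(−1.840/3.0) = 46%.
- Patient 3 is also short of 4 weeks with probability 1 − exp(−x)(1 + x), where x = w/3.3. This gives 3% at x = 0.279 and 11% at x = 0.558. Usually at most one patient's 4-week data would be missing.

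**Time to the interim analysis.** From patient 4's entry to patient 10's entry at even pace: 6 × 3.3 = 19.8 months (6 × 3.0 = 18.0 with 12-month follow-up). Six more patients, 6/20 = 30%, enter in that time.

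**What four patients can show.** P(at least 1 event) = 1 − (1 − p)^4. P(at least 2) = 1 − (1 − p)^4 − 4p(1 − p)^3. The true rates p are assumed.

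| True rate p | At least 1 of 4 | At least 2 of 4 |
|---|---|---|
| 10% | 34% | 5% |
| 20% | 59% | 18% |
| 30% | 76% | 35% |
| 50% | 94% | 69% |

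With 0 events in 4, the one-sided 95% upper bound is 1 − 0.05^(1/4) = 52.7%.

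**The case against.** The strongest reply is that silence in statistical sections is weak evidence. The text available jumps from section 3 to 12 and from 12 to 14. Hold and stopping rules would often sit in sections 4–11 or 13. This stands, and it limits the point to the sections available. A reader might infer that the trial has no safety hold at all; the documents do not support that.

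Second, 12.5 has adverse events, examination and imaging monitored at visits in an open-label, single-center study, so a serious event in any of the four would be seen when recorded. This also stands. A reader might infer that patients 5 to 10 are treated with nobody looking at safety; that is wrong. What is missing is a stated joint judgement before patient 5.

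Third, the shunt data go to the FDA for review, so an outside check before patient 5 is a natural reading. The text does not say that the review must finish or be favourable. Even a completed review would, as written, cover shunt data and not adverse events.

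Fourth, slow accrual would usually supply the post-treatment data anyway. That is true at the even pace. It makes a review nearly free but does not cause one to happen.

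Finally, it is tempting to call the interim analysis the first look at pooled adverse events, about 20 months after patient 4. It is the first one stated in the sections available. The footer in 14.5 shows a one-year IRB approval window, which suggests periodic renewal, though its content is not given.

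**Conclusion.** The point holds in a limited form. In the sections available, the lead-in has a stated safety purpose, but the condition set for patient 5 rests only on pre-treatment shunt data and could be met before patient 4 is treated or observed. It is a stated gate tied to data that cannot answer the safety question, so more than detail is missing.

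The practical size is modest. At the planned even pace all four patients would have passed 4 weeks. The gap matters mainly when patients arrive close together: at most about 24–43% with 6-month follow-up and the other assumptions listed, and less if patient 5 also has MAA or FDA review takes time. These percentages are chances that follow-up is short when patient 5 is ready, not chances of harm. The reading of the text depends on none of them.

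A four-patient review would itself be limited: no events would still be compatible with a true rate up to 52.7%. It can catch common early toxicity and little else. Confidence is medium because sections 4–11 and 13 could not be checked.

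**What to change.** Leave the shunt submission and the MAA rule on their present schedule. Add a separate condition to 12.5 and 14.2, along these lines:

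*Patient 5 will not be scheduled for 90Y until all four lead-in patients have been treated and the investigator and sponsor have reviewed their adverse events and 4-week imaging. The decision to proceed, change the dosing plan or hold will be recorded.*

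The sponsor should fix the hold criterion in advance, for example any treatment-related serious infection or splenic abscess. The table of one-event and two-event probabilities shows what each threshold would catch. The 4-week point is proposed because 2.1 already schedules imaging then. The plan does not say that 4 weeks is long enough for infection or abscess to appear, so the sponsor should confirm the window.

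The cost is protocol wording, one listing of data already collected, and a possible wait for patient 5. The condition would be met 4–12 weeks after patient 4's shunt study: 4 weeks of observation, plus an assumed 0–4 weeks from MAA to 90Y and an assumed 0–4 weeks for review. At even accrual (14.3 weeks between patients, or 13.0 with 12-month follow-up) this is absorbed. With exponential gaps of mean 3.3 months, patient 5 would wait with probability 24% if the condition takes 4 weeks, 43% if 8 weeks, and 1 − exp(−2.760/3.3) = 57% if 12 weeks.

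If an equivalent rule already exists in a section not available here, a cross-reference from 12.5 and 14.2 is all that is needed.

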14.3 Demographic and Baseline Characteristics

Demographics and baseline characteristics must include age, gender, race, ethnicity, concomitant medications, prior therapy, past medical history, and prior surgical history. Ancillary information can be noted by the clinical coordinator as appropriate.

14.4 Safety and Outcome Analysis

Clinical and outcome measures will be compared to baseline.

14.5 Duration of Procedure

Parameters to be recorded include during of procedure, number of TheraSphere® vials used,

radiation exposure, catheter/wire used and amount of contrast.

IRB #: STU00203772 Approved by NU IRB for use on or after 7/20/2020 through 7/19/2021.

Version 25 5.7.202022 5/7/19

23

14.6 Laboratory evaluations

Summary statistics for baseline and change from baseline will be summarized.

